The MMRM model will be implemented using SAS PROC MIXED. A restricted maximum likelihood (REML) will be used. The Kenward-Roger³ approximation will be used to estimate the denominator degrees of freedom and adjust standard errors. An appropriate covariance matrix will be used to model the within patient errors until there are no convergence issues in the following order: 1) unstructured, 2) Toeplitz, 3) autoregressive [1], 4) compound symmetry, 5) variance components. For analyses of multiple imputed datasets, this selection will continue until analyses for all imputations converge.

The treatment of missing data will be addressed using pattern mixture model methodology. Within each treatment, 4 data patterns will be defined as follows:

- Pattern 1: will include patients who completed treatment on study drug
- Pattern 2: will include patients who discontinue treatment early due to AEs
- Pattern 3: will include patients who discontinue treatment early due to lack of therapeutic efficacy (LOTE)
- Pattern 4: will include patients who discontinue treatment early due to reasons other than AE event or LOTE.

The pattern mixture model methodology will be implemented using SAS procedures MI and MIANALYZE. Specifically, the following steps will be followed:

- Intermittent missing data will first be imputed using the Markov Chain Monte Carlo (MCMC) method implemented with the SAS MI procedure, which is appropriate for non-monotonic missing data.
- Data for patients who discontinues early will be multiply imputed as follows:
 - If the patient discontinues due to AE (pattern 2) or LOTE (pattern 3), then missing data will be assumed to follow a distribution similar to the baseline values observed in the patient's randomized treatment.
 - If the patient discontinues due to reasons other than AE or LOTE (pattern 4), at each time point, missing data will be assumed to follow a distribution similar to scores for patients that are still in the study and randomized to the same treatment group.
- Results of the MMRM on the multiply imputed data will be summarized using the SAS MIANALYZE procedure using Rubin's rule.

A detailed plan of the above procedure is included as an attachment in Section 16.1.

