- Combine datasets from 2 and 3 with all data imputed and keep for Step 5.

Step 4 - Impute missing data due to reasons other than AE or LOTE

If the patient discontinues due to reasons other than AE or Lack of Efficacy, at each time point, missing data will be assumed to follow a distribution similar to scores for patients who are still in the study and randomized to the same treatment group.

- To impute missing data at the first week x with any missing data not due to AE/LOTE, the following will be performed to the MONOTONIC dataset:
 - Split the MONOTONIC data into 2 datasets
 - 1) Non-missing at Week x or missing at Week x and discontinued treatment not due to AE/LOTE
 - 2) Missing at Week x and discontinued treatment due to AE/LOTE – discard data
 - Sort dataset (1) by imputation and subject number
 - Impute the missing data at week x in dataset (1) as follows:

```
proc mi data=DATA1 out=WEEKx seed=543571857 n impute=1;
by Imputation ;
var TRTPN STRATAN BASE NRSWEEK1-NRSWEEKx;
monotone regression;
run;
```
 - Set any imputed values <0 or >10 to 0 and 10 respectively.
- To impute missing data at the next week y with any missing data not due to AE/LOTE, the following will be performed to the WEEKx dataset:
 - Split the WEEKx data into 2 datasets

- 3) Non-missing at Week y or missing at Week y and discontinued treatment not due to AE/LOTE
- 4) Missing at Week y and discontinued treatment due to AE/LOTE – discard data
 - Sort dataset (3) by imputation and subject number
 - Impute the missing data at week y in dataset (3) as follows:

```
proc mi data=DATA3 out=WEEKY seed=543571857 n impute=1;
by _Imputation_;
var TRTPN STRATAN BASE NRSWEEK1-NRSWEEKx;
monotone regression;
run;
```
 - Set any imputed values <0 or >10 to 0 and 10 respectively.

- Continue in similar fashion until no missing data with dataset including either completers or those that discontinued treatment not due to AE/LOTE.

Step 5 – Combine datasets back together and re-structure back as per ADaM

Combine final datasets from Steps 3 and 4. Sort by imputation and subject number. Re-structure dataset to be univariate with a Week (AVISITN = 1, 2,3 ,4 ,5 ,6 7, 8) and AVAL (using NRSWEEK1 to NRSWEEK8) and CHG (AVAL-BASE) variable. (MMRMDATA)

Step 6 – Perform MMRM on each imputed dataset

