The primary efficacy variable will be analyzed using a mixed effect model with repeated measures (MMRM). The model will contain treatment (placebo vs CR845), treatment-by-week interaction as fixed effects, baseline value and OA joint (hip vs knee) as covariates, and patient as a random effect.

```
proc mixed data=MMRMDATA;
by _Imputation_;
class TRTP AVISITN STRATA SUBJID;
model CHG = TRTP|AVISITN STRATA BASE /ddf=kr;
repeated AVISITN/SUBJECT=SUBJID type=un;
lsmeans TRTP*AVISITN/diff;
ods output Diffs=DIFF_MI LSMeans=LSM_MI;
run;
```

Check log to ensure that there are no convergence problems across all 100 analyses. If so then use different covariance structures in the following order until this is achieved:

type=toep

```
type=ar(1)  
type=cs  
type=vc
```

Extract 2 separate datasets from DIFF_MI and LSM_MI selecting the LS means (and standard errors) and difference between LS means (and standard errors) at Week 8 only. (DIFF_MI8 and LSM_MI8).

Step 7 – Combine MMRM results using Proc MIANALYZE

Use PROC MIANALYZE to obtain estimates of LS means and differences and 95% CIs.

```
proc mianalyze data=DIFF_MI8;  
model effects estimate;  
stderr sdterr;  
ods output ParameterEstimates=DIFF_MIAN8;  
run;  
  
proc mianalyze data=LSM_MI8;  
model effects estimate;  
by TRTP;  
ods output ParameterEstimates=LSM_MIAN8;  
run;
```

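### In the SAP's primary-analysis code (16.1, Step 4), the repeat PROC MI call for week y lists variables only to week x, contradicting its own text and the Pattern 4 rule in Section 10.1

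*SAP*

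**What the plan says.** SAP Section 10.1 gives the Pattern 4 rule: "at each time point, missing data will be assumed to follow a distribution similar to scores for patients that are still in the study", within the same randomized arm. It points to Section 16.1 for the detailed plan of that procedure.

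Section 16.1 Step 4 turns the rule into code. The first call deals with week x, the first week with a Pattern 4 gap, and its variable list ends at that week. The next part opens with "To impute missing data at the next week y with any missing data not due to AE/LOTE" and introduces its call with "Impute the missing data at week y in dataset (3) as follows". The call begins "proc mi data=DATA3 out=WEEKY seed=543571857", so its output is named for week y. Its variable list is nevertheless "var TRTPN STRATAN BASE NRSWEEK1-NRSWEEKx", the same as in the first call. The step ends with the instruction "Continue in similar fashion until no missing data with dataset including either completers or those that discontinued treatment not due to AE/LOTE".

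At each week, Step 4 drops records that are missing because of AE or LOTE before it imputes. Step 3 fills those patients separately, with random draws using the arm's baseline mean and SD. They rejoin the data in Step 5.

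Step 6 then fits "model CHG = TRTP|AVISITN STRATA BASE /ddf=kr" with an unstructured covariance. Section 10.1 requires Kenward-Roger. In Step 7 the first PROC MIANALYZE call has `stderr sdterr`, and the second, for the LS means, has no STDERR statement.

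**The concern.** PROC MI imputes only the variables in its VAR list. A call meant for week y whose list stops at week x has nothing to fill, and week y stays missing. If the same line is reused for each later week, the gap runs through to Week 8, the primary time point.

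The slip could pass unnoticed. The MMRM accepts missing weeks, and the only log check that Section 16.1 specifies is for convergence. The model would then handle Pattern 4 patients under a different assumption from the stated one. By that stage the data include AE and LOTE patients carrying baseline-level scores, which Step 4 deliberately keeps out of the Pattern 4 regressions.

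The same analysis yields the stage-wise statistics for the Cui-Hung-Wang test (SAP 10.1). The stage 1 LS-mean difference and standard error drive the sample size re-estimation (SAP Section 6). A literal reading could therefore reach the interim as well as the final result.

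**Working it through.** **1. The plan's own figure.** The documents give no dropout rate and no expected Pattern 4 count. The one design figure that can be checked is the power in the Protocol synopsis: 270 and 135 patients, effect size 0.343, two-sided 5%, power above 90%.

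- 0.343 / √(1/135 + 1/270) = 0.343 / 0.1054 = 3.254
- Power = Φ(3.254 − 1.960) = Φ(1.294) = 0.902 (0.901 by noncentral t)

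The figure reproduces. With an assumed SD of 2.0 it corresponds to 0.343 × 2.0 = 0.686 NRS points, used below as the true effect.

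**2. Trace of Step 4.**

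| | First call | Repeat call |
|---|---|---|
| Stated target | week x | week y |
| Data split on | week x | week y |
| Output dataset | WEEKx | WEEKY |
| List ends at | NRSWEEKx | NRSWEEKx |

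After the first call, week x is complete for everyone kept. The printed repeat list therefore contains no missing value. Executed literally, the share of Pattern 4 patients without a Step 4 value at Week 8 is 100% if x < 8 and 0% if x = 8. In 500 simulated trials of 405 patients, with dropout spread evenly over the weeks (an assumption), x was week 1 in 493 and week 2 in 7.

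**3. What fills the gap.** The rule in Section 10.1 is that missing scores "follow a distribution similar to scores for patients that are still in the study and randomized to the same treatment group". A likelihood MMRM also works under missing at random, so it comes close. It is not identical, because after Step 5 it also learns from the AE and LOTE patients' imputed baseline-level scores.

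**4. Size, large samples.** Assumptions: baseline mean 7 and SD 1.2; on-treatment SD 2.0; placebo improvement 1.5 points by Week 8; dropout timing unrelated to outcome. Each scenario used four sets of 120,000 patients at 2:1. The MMRM was approximated by sequential regressions. Dropout is given as placebo/CR845 in percent; differences are CR845 minus placebo at Week 8.

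| AE; LOTE; other | List to y | List to x | Shift |
|---|---|---|---|
| 5/12; 8/5; 10/10 | −0.5079 | −0.4939 | 0.0140 (3%) |
| 5/12; 8/5; 20/20 | −0.5147 | −0.4812 | 0.0335 (7%) |
| 5/12; 8/5; 10/20 | −0.5204 | −0.4576 | 0.0628 (12%) |
| 3/20; 5/5; 15/15 | −0.2562 | −0.1964 | 0.0598 (23%) |

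**5. Size, trial-sized samples.** This used 405 patients, 150 trials per scenario, and all Pattern 4 gaps left unfilled.

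- Placebo/CR845 AE 5/15, LOTE 8/5, other 12/12: −0.65 against −0.62, a shift of 0.03 (5%).
- AE 5/20, LOTE 10/5, other 20/20: −0.57 against −0.50, a shift of 0.07 (12%).
- A lower-dropout scenario: about 1% smaller.

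**6. Could Pattern 4 be common?** Protocol 8.10 discontinues anyone who misses more than one dose in titration, which is neither AE nor LOTE. Titration has 28 × 2 = 56 doses. With independent misses at rate p, the chance of two or more is 1 − (1−p)^56 − 56p(1−p)^55. This gives 11% at p = 1% and 31% at p = 2%. Both values of p are assumptions.

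The code was not run in SAS. The simulations address the point estimate only, not the standard error, power or type 1 error.

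**The case against.** The strongest reply is that the plan already says what to do. The sentence above the call names week y, the output is named for week y, the first call shows the pattern to follow, and the step is not finished while anything is missing. The week labels are placeholders, so a programmer must edit the line before it can run. SAP Section 13 requires all statistics to be validated with two independent programs, which gives a second chance to catch the slip. The neighbouring syntax errors would probably fail visibly and bring someone back to this code.

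Most of this stands, and it sets the severity. A reader might infer from the printed line that the primary analysis never imputes Week 8 for most patients who stop for other reasons, or that the Pattern 4 rule is abandoned. The documents do not support that. Section 10.1 states the rule for each time point, Section 16.1 is presented as the detail of that procedure, and the text of Step 4 orders imputation until nothing is missing. "Most" fits neither case in the trace: the literal line affects all Pattern 4 patients or none, depending on x.

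The reply does not remove the contradiction. The stopping condition is prose with no programmed check, and both programmers would work from the same attachment.

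**Conclusion.** The concern holds as a code error. One line of the primary-analysis program disagrees with the text around it and with Section 10.1. Executed literally with x before Week 8, it leaves every Pattern 4 patient without a Step 4 value after week x, and the MMRM supplies a similar but different assumption.

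In the scenarios tried, the Week 8 difference moved toward zero by about 0.01 to 0.07 NRS points. These figures rest on assumed dropout rates, SD, correlation and treatment effect. The larger shifts came from scenarios with higher CR845 AE dropout and 15% to 20% other dropout in at least the CR845 arm. Movement toward zero was seen in every scenario but is not shown in general.

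Severity is minor to moderate. The point is worth correcting because it sits in the primary-endpoint program and costs almost nothing. It is not evidence that the planned primary analysis omits Pattern 4 imputation.

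**What to change.** In SAP 16.1 Step 4, end the variable list of the week-y call at `NRSWEEKy`. Turn the existing stopping condition into a programmed check, before Step 5, that no value from `NRSWEEK1` to `NRSWEEK8` is missing in any imputed dataset.

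In the same revision:

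- Change `/ddf=kr` to `/ddfm=kr`, so that the code requests the Kenward-Roger method required by Section 10.1.
- Correct `stderr sdterr` to `stderr stderr`.
- Add a STDERR statement to the LS-means PROC MIANALYZE call. This concerns the per-arm means, not the primary contrast.

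Split keywords such as `n impute` may come from reading the PDF and are not counted here. The cost is a few characters of code and one check, with no change to design, data collection or sample size. It should be done before the program is run, including for the interim assessment.
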